## 9.4. Atezolizumab

## 9.4.1. Supply

Atezolizumab (MPDL3280A) is an investigational agent and will be supplied free-of-charge from Genentech.

Page 71 of 113

## 9.4.2. Formulation

The Atezolizumab drug product is provided in a single-use, 20-cc USP/Ph. Eur. Type 1 glass vial as a colorless-to-slightly-yellow, sterile, preservative-free clear liquid solution intended for IV administration. The vial contains ~20 mL (1200 mg) of Atezolizumab solution. The Atezolizumab drug product is formulated as 60 mg/mL Atezolizumab in 20 mM histidine acetate, 120 mM sucrose, 0.04% polysorbate 20, pH 5.8.

Atezolizumab must be refrigerated at 2°C-8°C (36°F-46°F) upon receipt until use. Vials should not be used beyond the expiration date provided by the manufacturer. No preservative is used in the Atezolizumab drug product; therefore, each vial is intended for single use only. Discard any unused portion of drug left in a vial. Vial contents should not be frozen or shaken and should be protected from direct sunlight. For further details on the storage and preparation of Atezolizumab, see the Investigator's Brochure.

## 9.4.3. Dosage, Administration, and Storage

The dose level of Atezolizumab to be tested in this study is 840 mg administered by IV infusion every 2 weeks (14 [± 2] days). Atezolizumab will be delivered in infusion bags with IV infusion lines that have product contacting surfaces of polyvinyl chloride (PVC) or polyolefin and 0.2 um in-line filters (filter membrane of polyethersulfone [PES]). No incompatibilities have been observed between Atezolizumab and PVC or polyolefin infusion materials (bags or infusion lines).

## 9.5. Drug Accountability

Clinical drug supply must be accounted for and patients will be asked to return all unused study drug and packaging on a regular basis, at the end of the study or at the time of study drug discontinuation. Accountability for the drug at all study sites is the responsibility of the principal investigator and designated Pharmacy representative. The investigator will ensure that the investigational drug is used only in accordance with this protocol. Drug accountability records indicating the drug's delivery date to the site, inventory at the site, use by each patient, and destruction/disposal per institutional policy will be maintained by the clinical site. Accountability records will include dates, quantities, lot numbers, expiration dates, and patient numbers.

At the conclusion of the study, and, as appropriate during the course of the study, the investigator will return all used and unused study drug, packaging, drug labels, and a copy of the completed drug accountability ledger to Genentech.

## 10. CORRELATIVE/SPECIAL STUDIES

#### 10.1. Overview

The correlative studies will focus on:

- 1) Pharmacodynamic evaluation of the effect of Cobimetinib and Idasanutlin using paired biopsies;
- 2) Evaluation of the effects of MEK and MDM2 inhibition on the tumor-immune microenvironment prior to initiating Atezolizumab;
- 3) Evaluation of the effects of MEK and MDM2 inhibition on the peripheral blood T cell repertoire and immunophenotype before and after initiating Atezolizumab; and
- 4) Correlation of items (1 3) with clinical response of the combination.

#### 10.2. **Blood Samples**

Tubes should be packed according to the **Lab manual** and sent immediately (within 24 h).

## 10.2.1. Specimen collection

Peripheral blood will be collected in patients prior to initiating Cobimetinib or Idasanutlin (PRE-Bx), and after 7-14 days of Cobimetinib or Idasanutlin, prior to adding on Atezolizumab (POST-Bx). The molecular correlates for each biological sample/time point are listed below.

Parameter	Cycle 1 Day 1 (PRE)	Cycle 1 Day 15 (POST)	Cycle 3 Day 1	End of Treatment
cfDNA	X	X	X	X
Flow Cytometry	X	X	X	X
HLA Typing	X			
Exome-seq (germline)	X			

Details on specimen handling can be found in the Lab Manual.

## 10.2.2. Specimen processing

Correlate	Sample Source	Test	Needs immediate specialized processing	Needs immediate shipping	
Exome-seq	Buffy coat	WBC DNA/NGS	NO		
HLA-typing	Bully Coat	WBC DNA/NGS	140		
CyTOF/Flow cytometry	Cyropreserved Ficoll-separated blood	PBMCs	YES (refer to Lab	NO	
cfDNA	Blood, platelet poor plasma (PPP)	Cell free DNA/NGS	Manual)		

# \*\*Specimens should be mailed to arrive from Monday 8AM through Friday 1PM\*\*

## 10.3. Tissues Samples

At screening: patients will provide a signed informed consent form prior to any study related activities. Patients with known *TP53* mutation status (by previously performed NGS or cfDNA) will not be required to wait to initiate study treatment provided all other screening procedures have been completed. For patients without known *TP53* mutation status, an archival tissue (FFPE from primary or metastatic lesion) should be sent to the Sponsor (see sections 10.3.1 – 10.3.3 for details on tissue submission requirements and testing procedures), and once tissue is received, results for *TP53* status will take an average of 2 weeks and will be communicated to the site.

On study: Fresh tumor biopsies will be collected in patients (a) prior to initiating Cobimetinib or Idasanutlin (PRE-Bx), and (b) after 15 days of Cobimetinib or Idasanutlin but prior to adding on Atezolizumab (POST-Bx). One tumor core will be fixed for IHC analysis, while two additional cores will be snap-frozen for RNA and DNA extraction where feasible. The fresh biopsies will follow guidelines as listed in the **Lab Manual**. The molecular correlates for each biological sample/time point are listed below.

Correlate	Sample Source	Test	Needs immediate specialized processing	Needs immediate shipping
TILs				
CD8				
CD4				
HLA-A (MHC-I)	FFPE tumor			
IHC	biopsy	IHC/multiplexed IF		
HLA-DR (MHC-II)	Diopsy		NO	NO
IHC				
FoxP3				
PD-L1				
RNA-seq	Fresh frozen	RNA		
Exome-seq	tumor biopsy	DNA		

Parameter	Prior to Cycle 1 Day 1	Cycle 1 Day 15
Immunohistochemistry (IHC) Analysis	X	X
RNA-seq	X	X
Exome-seq (tumor)	X	
TCR Sequencing	X	X

Tissue specimen labeling, documentation and shipment

- Label ALL specimens before freezing
- If sample comes in contact with contaminate, make note in information section of paperwork.
- Enter time core biopsy was collected on paperwork.
- Label each collection containers with Patient ID sequence number/code letter, Medical Record #, site and location of biopsy, date and time.
- Ship specimens along with Tissue/Blood Registration Form directly to:

[name]. Ph.D [name] [name] Office [contact]

Research Lab [contact]

The specimens will be logged in as a consented specimen and either be stored frozen or as paraffin-embedded tissue and available for molecular pathology studies.

- \*\*\*All frozen tissue should be sent in a cooler with ample volume of dry ice.
- \*\*\*All formalin-fixed paraffin embedded tissue and/or slides should be sent in a cooler with cold packs (except in winter months) to avoid melting of the paraffin leading to the tissue falling off the slides.
- \*\*These procedures are essential to prevent compromise of the tissue analyses.
- \*\*Specimens should be mailed to arrive from Monday 8AM through Friday 1PM\*\*

#### 10.4. **Quality control**

First, [name] or her designee (Pathology) will be examining tumor content of the frozen tissue by cutting a frozen H&E section from the tissue. To be adequate for the correlative studies, the invasive tumor area should be at least 5 mm x 5 mm and contain 20% tumor cellularity. If the biopsy contains tumor/immune content >40%, entire 10um sections will be used for RNA purification using the Promega Maxwell 16 automated method.

Purified RNA will be subjected to RNA-sequencing for whole-transcriptome profiling. Biopsies containing <40% will be macrodissected from sequential slides to enrich for the tumor portion, and RNA purified as above.

For DNA extraction, there are no expected tumor changes at the exome level, and so only one time point will be analyzed, preferably PRE-Bx. Tumor content >80% will be targeted, using the whole section/macrodissection scheme above.

#### 10.5. **Genetic Testing**

Participants will be given information as part of the informed consent process that samples will be used for research tests that will include genetic studies and testing. The intent is not to give participants (or his/her medical providers) the results of any testing done for research purposes; however, incidental germline (heritable) mutations may be identified of which a participant may or may not already be aware. In the case that an incidental genetic finding is identified, the Protocol Chair of this project will be notified. The possible decisions for handling incidental findings may include notification of the participant (and provider); recommendation for genetic counseling, which may or may not include genetic testing (e.g., if the finding was not done in a CLIA certified laboratory); or, neither. In general, a member of the participant's treating team will be given the information to help with notification. In all cases, the current policy of the local/participating site IRB, as applicable, will be followed and any additional approvals that may be required prior to participant notification will be secured in advance.

### 11. SPECIMEN BANKING

The study Protocol Chair and collaborators have approval to use all research bio-specimens collected during the conduct of this trial to address the research questions described in the protocol document. All future use of residual or repository specimens collected in this trial for purposes not prospectively defined will require review and approval by the Protocol Chair, whether the specimens are stored in a central site or at a local institution in a virtual repository.

### 12. MEASUREMENT OF EFFECT

For the purposes of this study, patients should be re-evaluated for response after every two cycles. Response and progression will be evaluated in this study using the international criteria proposed by the revised Response Evaluation Criteria in Solid Tumors (RECIST) Committee (version 1.1). Changes in only the largest diameter (unidimensional measurement) of the tumor lesions are used in the RECIST criteria.

#### 12.1. **Definitions**

Evaluable for toxicity: All patients will be evaluable for toxicity from the time of their first administration of study treatment drugs.

Evaluable for objective response: Only those patients who have measurable disease present at baseline, have received at least one cycle of therapy, and have had their disease re-evaluated will be considered evaluable for response. These patients will have their response classified according to the definitions stated below.

#### 12.2. **Disease Parameters**

### 12.2.1. Measurable

Tumor lesions: Must be accurately measured in at least one dimension (longest diameter in the plane of measurement is to be recorded) with a minimum size of:

- 10 mm by CT scan (CT scan slice thickness no greater than 5 mm)
- 10 mm caliper measurement by clinical exam (lesions which cannot be accurately measured with calipers should be recorded as non-measurable)
- 20 mm by chest X-ray

Malignant lymph nodes: To be considered pathologically enlarged and measurable, a lymph node must be ≥15mm in short axis when assessed by CT scan (CT scan slice thickness recommended to be no greater than 5 mm). At baseline and in followup, only the short axis will be measured and followed.

### 12.2.2. Non-measurable

All other lesions, including small lesions (longest diameter <10mm or pathological lymph nodes of ≥10 to <15 mm in the short axis) as well as truly non-measurable lesions. Lesions considered truly non-measurable include: leptomeningeal disease, ascites, pleural or pericardial effusion, inflammatory breast disease, lymphangitic involvement of skin or lung, and abdominal masses/abdominal organomegaly identified by physical exam that is not measurable by reproducible imaging techniques.

## 12.2.3. Special considerations regarding lesion measurability

Bone lesions, cystic lesions, and lesions previously treated with local therapy require particular comment:

### 12.2.4. Bone lesions:

- Bone scan, PET scan or plain films are not considered adequate imaging techniques to measure bone lesions. However, these techniques can be used to confirm the presence or disappearance of bone lesions
- Lytic bone lesions or mixed lytic-blastic lesions, with identifiable soft tissue components, that can be evaluated by cross-sectional imaging techniques such as CT or MRI can be considered as measurable lesions if the soft tissue component meets the definition of measurability described above
- Blastic bone lesions are non-measurable

## 12.2.5. Cystic lesions:

- Lesions that meet the criteria for radiographically defined simple cysts should not be considered as malignant lesions (neither measurable nor non-measurable) since they are, by definition, simple cysts
- 'Cystic lesions' thought to represent cystic metastases can be considered as measurable lesions, if they meet the definition of measurability described above. However, if non cystic lesions are present in the same patient, these are preferred for selection as target lesions

#### 12.3. **Lesions with prior local treatment:**

Tumor lesions situated in a previously irradiated area, or in an area subjected to other locoregional therapy, are usually not considered measurable unless disease progression there has been demonstrated

### 12.3.1. Specifications by methods of measurements

### Measurement of lesions

[figure not shown]
All measurements should be recorded in metric notation, using calipers if clinically assessed. All baseline evaluations should be performed as close as possible to the treatment start and never more than 4 weeks before the beginning of the treatment.

### 12.3.2. Method of assessment

The same method of assessment and the same technique should be used to characterize each identified and reported lesion at baseline and during follow-up. Imaging based evaluation should always be done rather than clinical examination unless the lesion(s) being followed cannot be imaged but is/are assessable by clinical exam.

- Clinical lesions: Clinical lesions will only be considered measurable when they are superficial and ≥ 10 mm in diameter as assessed using calipers (e.g., skin nodules). For the case of skin lesions, documentation by color photography including a ruler to estimate the size of the lesion is suggested. When lesions can be evaluated by both clinical exam and imaging, imaging evaluation should be undertaken since it is more objective and may also be reviewed at the end of the study.
- ☐ Chest X-ray: Chest CT is preferred over chest X-ray, particularly when progression is an important endpoint, since CT is more sensitive than X-ray, particularly in identifying new

#### 12.4. **Response Criteria**

### 12.4.1. Target lesions

When more than one measurable lesion is present at baseline all lesions up to a maximum of five lesions total (and a maximum of two lesions per organ) representative of all involved organs should be identified as target lesions and will be recorded and measured at baseline. This means that in instances where patients have only one or two organ sites involved, a maximum of two and four lesions, respectively, will be recorded.

### 12.4.1.1. Evaluation of Target Lesions

Complete Response (CR): Disappearance of all target lesions. Any pathological lymph nodes (whether target or non-target) must have reduction in short axis to <10 mm.

Partial Response (PR): At least a 30% decrease in the sum of diameters of target lesions, taking as reference the baseline sum diameters.

Progressive Disease (PD): At least a 20% increase in the sum of diameters of target lesions, taking as reference the smallest sum on study (this includes the baseline sum if that is the smallest on study). In addition to the relative increase of 20%, the sum must

also demonstrate an absolute increase of at least 5 mm. (Note: the appearance of one or more new lesions is also considered progression).

Stable Disease (SD): Neither sufficient shrinkage to qualify for PR nor sufficient increase to qualify for PD, taking as reference the smallest sum of diameters while on study.

## 12.4.2. Non-target lesions:

All other lesions (or sites of disease) including pathological lymph nodes should be identified as non-target lesions and should also be recorded at baseline. Measurements are not required and these lesions should be followed as 'present', 'absent', or, in rare cases 'unequivocal progression'. In addition, it is possible to record multiple non-target lesions involving the same organ as a single item on the case record form (e.g. 'multiple enlarged pelvic lymph nodes' or 'multiple liver metastases').

#### **Evaluation of Non-Target Lesions** 12.4.2.1.

Complete Response (CR): Disappearance of all non-target lesions and normalization of tumor marker levels. All lymph nodes must be non-pathological in size (<10 mm in their short axis).

Non-CR/Non-PD: Persistence of one or more non-target lesion(s) and/or maintenance of tumor marker levels above the normal limits.

Progressive Disease (PD): Unequivocal progression of existing non-target lesions. (Note: the appearance of one or more new lesions is also considered progression).

## 12.4.3. Evaluation of Best Overall Response

The best overall response is the best response recorded from the start of the study treatment until the end of treatment taking into account any requirement for confirmation. On occasion a response may not be documented until after the end of therapy so protocols should be clear if post-treatment assessments are to be considered in determination of best overall response. Protocol must specify how any new therapy introduced before progression will affect best response designation. The patient's best overall response assignment will depend on the findings of both target and non-target disease and will also take into consideration the appearance of new lesions. Furthermore, depending on the nature of the study and the protocol requirements, it may also require confirmatory measurement. Specifically, in non-randomized trials where response is the primary endpoint, confirmation of PR or CR is needed to deem either one as the 'best overall response'.

Target Lesions	Non-Target Lesions	New Lesions	Overall Response
CR	CR	No	CR
CR	Non CR/Non PD	No	PR
CR	Not evaluated	No	PR
PR	Non PD or not all evaluated	No	PR
SD	Non PD or not all evaluated	No	SD
Not all evaluated	Non PD	No	NE
PD	Any	Yes or no	PD
Any	PD	Yes or no	PD
Any	Any	Yes	PD

CR=complete response, PR=partial response, PD=progressive disease, SD=stable disease, NE=not evaluable.

\* In exceptional circumstances, unequivocal progression in non-target lesions may be accepted as disease progression.

Note: Patients with a global deterioration of health status requiring discontinuation of treatment without objective evidence of disease progression at that time should be reported as "symptomatic deterioration". In these patients, every effort should be made to document the objective progression even after discontinuation of treatment.

# 13. Immune-Related Response Criteria (irRC)

#### 13.1. Introduction

Increasing clinical experience indicates that traditional response criteria (e.g., Response Evaluation Criteria in Solid Tumors, Version 1.1 [RECIST v1.1] and World Health Organization [WHO]) may not be sufficient to characterize fully activity in the new era of target therapies and/or biologics. In studies with cytokines, cancer vaccines, and monoclonal antibodies, complete response, partial response, or stable disease has been shown to occur after an increase in tumor burden as characterized by progressive disease by traditional response criteria. Therefore, conventional response criteria may not adequately assess the activity of immunotherapeutic agents because progressive disease (by initial radiographic evaluation) does not necessarily reflect therapeutic failure. Long-term effect on the target disease must also be captured. The immune-related response criteria (irRC) are criteria that attempt to do that by enhancing characterization of new response patterns that have been observed with immunotherapeutic agents (i.e., ipilimumab). (Note: The irRC only index and measurable new lesions are taken into account.)

#### 13.2. Glossary

Term	Definition
SPD	sum of the products of the two largest perpendicular diameters
Tumor burden	SPD index lesions + SPD new, measurable lesions
Nadir	minimally recorded tumor burden
irCR	immune-related complete response
irPD	immune-related progressive disease
irPR	immune-related partial response
irSD	immune-related stable disease
irBOR	immune-related best overall response

#### 13.3. **Baseline Assessment Using irRC**

- Step 1. Identify the index lesions (five lesions per organ, up to ten visceral lesions and five cutaneous lesions).
- Step 2. Calculate the SPD of all of these index lesions: SPD =  $\Sigma$  (Largest diameter of lesion i) × (Second largest diameter of lesion i).

#### 13.4. Post-baseline Assessments using irRC:

- Step 1. Calculate the SPD of the index lesions.
- Step 2. Identify new, measurable lesions ( $\geq 5 \times 5$  mm; up to five new lesions per organ: five new cutaneous lesions and ten visceral lesions).
- Step 3. Calculate the SPD of the new, measurable lesions.
- Step 4. Calculate the tumor burden: Tumor burden = SPDindex lesions + SPDnew. measurable lesions
- Step 5. Calculate the change in tumor burden relative to baseline and the change in tumor burden relative to nadir.
- Step 6. Derive the overall response using the table below.

Overall Response	Criterion
irCR	Complete disappearance of all lesions (whether measurable or not, and no new lesions) confirmed by a repeat, consecutive assessment $\geq$ 4 weeks from the date first documented
irPR	Decrease in tumor burden ≥ 50% relative to baseline confirmed by a consecutive assessment ≥ 4 weeks from the date first documented
irSD	Criteria for irCR, irPR, and irPD are not met; does not require confirmation
irPD	Increase in tumor burden $\geq$ 25% relative to nadir confirmed by a consecutive assessment $\geq$ 4 weeks from the date first documented

irCR = immune-related complete response; irPD = immune-related progressive disease;

irPR = immune-related partial response; irSD = immune-related stable disease.

#### 13.5. **Determination of Immune-Related Best Overall Response (irBOR)**

Once a patient has completed all tumor assessments, his/her irBOR may be determined:

Condition	irBOR
At least one irCR	irCR
At least one irPR and no irCR	irPR
At least one irSD and no irCR and no irPR	irSD
At least one irPD and no irCR, no irPR, and no irSD	irPD

irBOR = immune-related best overall response; irCR = immune-related complete response;

irPD = immune-related progressive disease; irPR = immune-related partial response;

irSD = immune-related stable disease.

## 14. Duration of Response

Duration of overall response: The duration of overall response is measured from the time measurement criteria are met for CR or PR (whichever is first recorded) until the first date that recurrent or progressive disease is objectively documented (taking as reference for progressive disease the smallest measurements recorded since the treatment started).

The duration of overall CR is measured from the time measurement criteria are first met for CR until the first date that recurrent disease is objectively documented.

Duration of stable disease: Stable disease is measured from the start of the treatment until the criteria for progression are met, taking as reference the smallest measurements recorded since the treatment started.

## 15. ADVERSE EVENT REPORTING REQUIREMENTS

#### 15.1. General

Adverse event collection and reporting is a routine part of every clinical trial. This study will use the descriptions and grading scales found in the NCI Common Terminology Criteria for Adverse Events version 5.0 (CTCAE v5.0) that is available at http://ctep.cancer.gov/reporting//ctc.html.

Information on all adverse events, whether reported by the participant, directly observed, or detected by physical examination, laboratory test or other means, will be collected, recorded, followed and reported as described in the following sections.

Adverse events experienced by participants will be collected and reported from initiation of study medication, throughout the study, and within 28 days (+/- 7 days) of the last dose of study medication. Participants who experience an ongoing adverse event related to a study procedure and/or study medication beyond 28 days (+/- 7 days) will continue to be contacted by a member of the study team weekly until the event is resolved, stabilized, or determined to be irreversible by the participating investigator.

Participants should be instructed to report any serious post-study event(s) that might reasonably be related to participation in this study. The investigator should notify the IRB (as per institutional guidelines) and any other applicable regulatory agency of any unanticipated death or adverse event occurring after a participant has discontinued or terminated study participation that may reasonably be related to the study drugs.

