#### 15.2. **Definitions**

15.2.1. Adverse Event (AE)

An AE is any unfavorable and unintended sign (including an abnormal laboratory finding), symptom, or disease temporally associated with the use of an investigational medicinal product protocol-imposed regardless (IMP) or other intervention. attribution. This includes the following:

- AEs not previously observed in the subject that emerge during the protocol-specified AE reporting period, including signs or symptoms associated with metastatic ER+ breast cancer that were not present prior to the AE reporting period.
- Complications that occur as a result of protocol-mandated interventions (e.g., invasive procedures such as cardiac catheterizations)
- If applicable, AEs that occur prior to assignment of study treatment associated with medication washout, no treatment run-in, or other protocol-mandated intervention.
- Preexisting medical conditions (other than the condition being studied) judged by the investigator to have worsened in severity or frequency or changed in character during the protocol-specified AE reporting period.

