### 15.3.1. Adverse Event Reporting Period

The study period during which AEs and SAEs as described in section 13.2 where the patient has been exposed to Genentech product must be reported. Reporting period begins after informed consent is obtained and initiation of study treatment and ends 30 days following the last administration of study treatment or study discontinuation/termination, whichever is earlier. After this period, investigators should only report SAEs that are attributed to prior study treatment.

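### The adverse-event windows open at first dose and so exclude complications of the protocol's own pre-dose research biopsy, and the end of the window is stated in two incompatible ways

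*Combined protocol and SAP*

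**What the plan says.** **Start of collection.** Section 15.1: "Adverse events experienced by participants will be collected and reported from initiation of study medication". Section 15.3.1, which covers both AEs and SAEs in patients exposed to the supplied drugs: "Reporting period begins after informed consent is obtained and initiation of study treatment and ends 30 days following the last administration of study treatment". Section 12.1 likewise makes patients evaluable for toxicity from first administration.

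**What counts as an AE.** Section 15.2.1 includes "Complications that occur as a result of protocol-mandated interventions", with no time limit on that item and with an invasive procedure as its example. The next item adds: "If applicable, AEs that occur prior to assignment of study treatment associated with medication washout, no treatment run-in, or other protocol-mandated intervention".

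**The pre-dose procedure.** Section 10.3 and the Section 6 calendar place a fresh tumor biopsy (PRE-Bx) before the first dose of cobimetinib or idasanutlin. Calendar note 5 allows excisional, incisional or core needle biopsy in consenting patients with a suitable lesion. Section 5.1 requires research-only procedures to follow consent.

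**End of collection.** Section 15.1 collects events "within 28 days (+/- 7 days) of the last dose of study medication". Section 15.3.1 ends 30 days after the last administration "or study discontinuation/termination, whichever is earlier".

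**Rules without a start date.** Section 17.3 sends every SAE to the Coordinating Center whatever its relation to study drug. Section 17.3.1 sends AEs and SAEs to the IRB under institutional standards. The item on deaths in 17.2.2, by contrast, covers deaths within the AE reporting period.

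**The concern.** A definition and a collection window should cover the same events. Here the definition takes in harm from procedures that the protocol requires, while both windows start after the first such procedure has been done. A bleed or pneumothorax from the PRE-Bx would be an AE under 15.2.1, but a site following 15.1 literally would not record it. A patient harmed badly enough not to start treatment would never enter either window.

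At the other end, sites in a multicenter trial can follow either of two closing rules and return different data for comparable patients. The adverse event profile is a secondary endpoint in each arm, so its content should not depend on which section a site reads. What is at stake is a complete account of the burden of the research biopsy for those overseeing the trial, and uniform safety data across sites.

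**Working it through.** The plan gives no figure to reproduce. The check sets the rules side by side, with simple day counts.

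**Start.**
- Consent comes first, since research-only procedures must follow it (5.1).
- The PRE-Bx comes next, in the pre-treatment column of the calendar, within 4 weeks before treatment (Section 6, note 1).
- First dose follows. The 15.1 and 15.3.1 windows and toxicity evaluability (12.1) all open here.
- The uncovered interval therefore runs from biopsy to first dose and can last up to about 4 weeks.
- The second biopsy, on Cycle 1 Day 15, comes after first dose. It lies inside both windows and is not affected.

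**Which pre-dose events have a rule?**
- *Non-serious complications:* AEs by 15.2.1, outside 15.1 and 15.3.1. Section 17.3.1 leaves IRB reporting to institutional standards and does not itself create trial data collection. There is no clear collection rule.
- *Serious complications:* 17.3 taken alone requires them. Section 15.3.1, which defines the period, applies its first-dose start to SAEs as well. The two readings conflict.
- *Deaths:* 17.2.2 refers back to the AE reporting period, so a pre-dose death falls outside that item on its wording.
- *Patients biopsied but never dosed:* absent from the safety analysis, which is limited to those given at least one dose (synopsis, Study Assessments) or who began treatment (7.10).

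Section 15.1 itself continues follow-up of ongoing AEs related to a study procedure. Capturing procedure harm is therefore intended, and the start date defeats that intention for the PRE-Bx.

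**End, in days after last dose.**
- 15.1: 28 − 7 = 21 to 28 + 7 = 35.
- 15.3.1: 30, or the day of study discontinuation or termination if that comes first.
- Differences: 30 − 21 = 9 days, where 15.1 closes first; 35 − 30 = 5 days, where 15.1 closes last. If the patient leaves the study before day 30, 15.3.1 closes earlier still.

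**Related anchors.** Section 7.9 counts 28 (± 7) days from discontinuation for progression, and calendar note 6 counts from the End-of-Treatment visit. Section 8.6 lets atezolizumab continue alone after the partner drug stops, so it matters which drug's last dose starts the clock. Section 15.3.1 also cites section 13.2 for the AE definitions; in the current numbering that is the glossary of the immune-related response criteria.

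**The case against.** The strongest reply is that other provisions limit the loss, and much of that reply stands.

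- A reader might infer that biopsy complications are never reported. The documents do not support that. Section 17.3 requires all SAEs without a start date, 17.3.1 adds the IRB route, Section 21 has the DSMC review all SAEs quarterly, and the calendar assesses AEs throughout the study. For serious events the fair description is ambiguity.
- A reader might try to estimate the missed events by applying a complication rate to 66 + 18 = 84 patients. The documents give no rate. The 84 is also not a count of biopsied patients: calendar note 5 restricts biopsy to consenting patients with suitable lesions, and the table in 24.1 makes at least 6 patients treated at the recommended dose evaluable in Phase II as well.
- A reader might infer that late immune-related events are what the end rule loses. Section 15.3.1 keeps SAEs attributed to study treatment reportable after the window. Section 15.1 keeps weekly contact for ongoing related AEs and asks for related serious post-study events. Section 7.9 follows patients removed for toxicity.
- The clause on study discontinuation may be meant for patients who cannot be followed, as in 7.13. But the protocol elsewhere uses leaving the study loosely for stopping treatment (calendar note 7; 7.11), so that limit has to be written down.
- The drug safety objective is defined on dosed patients by design, so the start date does not bias that profile. It leaves research-procedure harm without a place.

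Two weaker replies do not remove the point. The pre-assignment item in 15.2.1 is conditional, but the item on protocol-mandated interventions is not. Day 30 does lie within days 21 to 35, but a range and a fixed day with an earlier cut-off remain different rules.

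**Conclusion.** Both inconsistencies stand. Complications of the PRE-Bx are AEs by definition and fall outside both windows for up to about 4 weeks: non-serious ones have no collection rule, and serious ones and deaths are subject to conflicting text. The end rules differ by up to 9 days in one direction and 5 in the other, or by more if study discontinuation comes first. The end-of-window exposure is mainly new non-serious events and events not attributed to treatment.

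This rests on reading 15.1 and 15.3.1 as the operative collection rules and on the PRE-Bx being done in the pre-treatment period as scheduled. It needs no assumed complication rate, and the number of events affected cannot be derived from the documents. The primary endpoint and sample size are untouched. The amendment is worth making because it is cheap and the safety data would otherwise vary with the section a site follows.

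**What to change.** Reconcile 15.1, 15.2.1, 15.3.1, the deaths item in 17.2.2, and 17.3:

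1. Collect AEs and SAEs, including deaths, caused by protocol-mandated procedures from informed consent, and all AEs from first dose.
2. List procedure-related events separately for patients who are never dosed, so that the drug safety population stays as defined.
3. State one end date in both 15.1 and 15.3.1, counted from the last dose of any study drug, and align 7.9 and calendar note 6 with it.
4. Limit the earlier-end clause in 15.3.1 to withdrawal of consent or loss to follow-up. Keep the existing provisions for attributed SAEs and ongoing related AEs.
5. Correct the section reference in 15.3.1.

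The cost is protocol wording, one eCRF field that marks an event as procedure-related and pre-dose, and a few additional reports. No change to the analysis of the primary endpoint is needed.
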